
CEA, $\mu\text{g/L}$
 
n
 
Mean (SD)
 
Median (IQR)
 
Min, Max
 
Clinically significant, n (%)
	
XXX
 
XX.X (XX.X)
 
XX.X (XX.X)
 
XX.X, XX.X
 
XX (XX.X)
	
XXX
 
XX.X (XX.X)
 
XX.X (XX.X)
 
XX.X, XX.X
 
XX (XX.X)
	
XXX
 
XX.X (XX.X)
 
XX.X (XX.X)
 
XX.X, XX.X
 
XX (XX.X)
	
XXX
 
XX.X (XX.X)
 
XX.X (XX.X)
 
XX.X, XX.X
 
XX (XX.X)

n: number of subjects; %: percentage of respective population pool treatment group; SD: standard deviation; IQR: interquartile range.

Table 7: Disease free survival and overall survival

	Modified intention-to-treat		Per-protocol	
	Aspirin (N=xxxx)	Placebo (N=xxxx)	Aspirin (N=xxxx)	Placebo (N=xxxx)
First recurrence, n (%)	xxx (xx.x)	xxx (xx.x)	xxx (xx.x)	xxx (xx.x)
Site of recurrence, n (%)				
Local	xxx (xx.x)	xxx (xx.x)	xxx (xx.x)	xxx (xx.x)
Anastomotic site	xxx (xx.x)	xxx (xx.x)	xxx (xx.x)	xxx (xx.x)
Lymph node	xxx (xx.x)	xxx (xx.x)	xxx (xx.x)	xxx (xx.x)
Peritoneum	xxx (xx.x)	xxx (xx.x)	xxx (xx.x)	xxx (xx.x)
Liver	xxx (xx.x)	xxx (xx.x)	xxx (xx.x)	xxx (xx.x)
Lungs	xxx (xx.x)	xxx (xx.x)	xxx (xx.x)	xxx (xx.x)
New primary	xxx (xx.x)	xxx (xx.x)	xxx (xx.x)	xxx (xx.x)
Others	xxx (xx.x)	xxx (xx.x)	xxx (xx.x)	xxx (xx.x)
Method of first recurrence diagnosis, n (%)				
Radiological imaging	xxx (xx.x)	xxx (xx.x)	xxx (xx.x)	xxx (xx.x)
Histology / cytology	xxx (xx.x)	xxx (xx.x)	xxx (xx.x)	xxx (xx.x)
Scope	xxx (xx.x)	xxx (xx.x)	xxx (xx.x)	xxx (xx.x)
Digital rectal examination	xxx (xx.x)	xxx (xx.x)	xxx (xx.x)	xxx (xx.x)
Others	xxx (xx.x)	xxx (xx.x)	xxx (xx.x)	xxx (xx.x)
Death, n (%)	xxx (xx.x)	xxx (xx.x)	xxx (xx.x)	xxx (xx.x)
Cause of death, n (%)				

Colorectal cancer	XXX (XX.X)	XXX (XX.X)	XXX (XX.X)	XXX (XX.X)
Other cancer	XXX (XX.X)	XXX (XX.X)	XXX (XX.X)	XXX (XX.X)
Other causes	XXX (XX.X)	XXX (XX.X)	XXX (XX.X)	XXX (XX.X)
Unknown	XXX (XX.X)	XXX (XX.X)	XXX (XX.X)	XXX (XX.X)
Presence of colon/rectal cancer at death, n (%)				
Yes	XXX (XX.X)	XXX (XX.X)	XXX (XX.X)	XXX (XX.X)
No	XXX (XX.X)	XXX (XX.X)	XXX (XX.X)	XXX (XX.X)
Unknown	XXX (XX.X)	XXX (XX.X)	XXX (XX.X)	XXX (XX.X)
Median follow-up time (95% CI), month	XX.X (XX.X-XX.X)	XX.X (XX.X-XX.X)	XX.X (XX.X-XX.X)	XX.X (XX.X-XX.X)
All tumour types				
Subjects with recurrence or who died without recurrence, n (%)	XXX (XX.X)	XXX (XX.X)	XXX (XX.X)	XXX (XX.X)
Median DFS time (95% CI), month	XX.X (XX.X-XX.X)	XX.X (XX.X-XX.X)	XX.X (XX.X-XX.X)	XX.X (XX.X-XX.X)
DFS rate at 3 years (95% CI), %	XX.X (XX.X-XX.X)	XX.X (XX.X-XX.X)	XX.X (XX.X-XX.X)	XX.X (XX.X-XX.X)
Difference in DFS rate at 3 years (95% CI), %	XX.X (XX.X-XX.X)	XX.X (XX.X-XX.X)	XX.X (XX.X-XX.X)	XX.X (XX.X-XX.X)
DFS rate at 5 years (95% CI), %	XX.X (XX.X-XX.X)	XX.X (XX.X-XX.X)	XX.X (XX.X-XX.X)	XX.X (XX.X-XX.X)
Difference in DFS rate at 5 years (95% CI), %	XX.X (XX.X-XX.X)	XX.X (XX.X-XX.X)	XX.X (XX.X-XX.X)	XX.X (XX.X-XX.X)
DFS hazard ratio (95% CI); p-value ¹	XX.X (XX.X-XX.X)	XX.X (XX.X-XX.X)	XX.X (XX.X-XX.X)	XX.X (XX.X-XX.X)
Adjusted DFS hazard ratio 1 (95% CI); p-value ²	XX.X (XX.X-XX.X); 0.XXX	XX.X (XX.X-XX.X); 0.XXX	XX.X (XX.X-XX.X); 0.XXX	XX.X (XX.X-XX.X); 0.XXX
Adjusted DFS hazard ratio 2 (95% CI); p-value ³	XX.X (XX.X-XX.X); 0.XXX	XX.X (XX.X-XX.X); 0.XXX	XX.X (XX.X-XX.X); 0.XXX	XX.X (XX.X-XX.X); 0.XXX
Median OS time (95% CI), month	XX.X (XX.X-XX.X)	XX.X (XX.X-XX.X)	XX.X (XX.X-XX.X)	XX.X (XX.X-XX.X)
OS rate at 3 years (95% CI), %	XX.X (XX.X-XX.X)	XX.X (XX.X-XX.X)	XX.X (XX.X-XX.X)	XX.X (XX.X-XX.X)
Difference in OS rate at 3 years (95% CI), %	XX.X (XX.X-XX.X)	XX.X (XX.X-XX.X)	XX.X (XX.X-XX.X)	XX.X (XX.X-XX.X)
OS rate at 5 years (95% CI), %	XX.X (XX.X-XX.X)	XX.X (XX.X-XX.X)	XX.X (XX.X-XX.X)	XX.X (XX.X-XX.X)

Difference in OS rate at 5 years (95% CI), %	XX.X (XX.X-XX.X)	XX.X (XX.X-XX.X)
OS hazard ratio (95% CI); p-value ¹	XX.X (XX.X-XX.X); 0.XXX	XX.X (XX.X-XX.X); 0.XXX
Adjusted OS hazard ratio 1 (95% CI); p-value ²	XX.X (XX.X-XX.X); 0.XXX	XX.X (XX.X-XX.X); 0.XXX
Adjusted OS hazard ratio 2 (95% CI); p-value ³	XX.X (XX.X-XX.X); 0.XXX	XX.X (XX.X-XX.X); 0.XXX
Colon cancer only		
Subjects with recurrence or who died without recurrence, n (%)		
Median DFS time (95% CI), month	XX.X (XX.X-XX.X)	XX.X (XX.X-XX.X)
DFS rate at 3 years (95% CI), %	XX.X (XX.X-XX.X)	XX.X (XX.X-XX.X)
Difference in DFS rate at 3 years (95% CI), %	XX.X (XX.X-XX.X)	XX.X (XX.X-XX.X)
DFS rate at 5 years (95% CI), %	XX.X (XX.X-XX.X)	XX.X (XX.X-XX.X)
Difference in DFS rate at 5 years (95% CI), %	XX.X (XX.X-XX.X)	XX.X (XX.X-XX.X)
DFS hazard ratio (95% CI); p-value ¹	XX.X (XX.X-XX.X); 0.XXX	XX.X (XX.X-XX.X); 0.XXX
Adjusted DFS hazard ratio 1 (95% CI); p-value ²	XX.X (XX.X-XX.X); 0.XXX	XX.X (XX.X-XX.X); 0.XXX
Adjusted DFS hazard ratio 2 (95% CI); p-value ³	XX.X (XX.X-XX.X); 0.XXX	XX.X (XX.X-XX.X); 0.XXX
Sub-distribution hazard ratio for first recurrence (95% CI); p-value ⁴	XX.X (XX.X-XX.X); 0.XXX	XX.X (XX.X-XX.X); 0.XXX
Sub-distribution hazard ratio for death due to other cancers (95% CI); p-value ⁴	XX.X (XX.X-XX.X); 0.XXX	XX.X (XX.X-XX.X); 0.XXX

n: number of subjects; %: percentage of respective population pool treatment group; CI: confidence interval; DFS: disease free survival; OS: overall survival.
¹P-values from log-rank test.

²Adjusted hazard ratio was estimated using Cox proportional hazard model with trial stratification factors (centre pooled by country (categorical), type of tumour (categorical) and type of adjuvant chemotherapy (categorical)) as covariates. P-values from stratified log-rank test stratified by the factors included as covariates in the Cox proportional hazard model.

³Adjusted hazard ratio was estimated using Cox proportional hazard model with trial stratification factors (centre pooled by country (categorical), type of tumour (categorical) and type of adjuvant chemotherapy (categorical)), time from surgery to first chemotherapy in days (continuous), type of surgery (categorical), chemotherapy duration (categorical) and age group (categorical) as covariates. P-values from stratified log-rank test stratified by the factors included as covariates in the Cox proportional hazard model.

⁴P-value from Fine and Gray's model.

Table 8: Results of multivariate Cox proportional hazard models on disease free survival and overall survival

	Modified intention-to-treat		Per-protocol	
	Adjusted Hazard Ratio (95% CI)	P- value	Adjusted Hazard Ratio (95% CI)	P-value
Disease free survival				
Treatment (Aspirin vs. placebo)	xx.x (xx.x-xx.x)	0.xxx	xx.x (xx.x-xx.x)	0.xxx
Country		0.xxx		0.xxx
Country 1 vs. Reference Country	xx.x (xx.x-xx.x)	0.xxx	xx.x (xx.x-xx.x)	0.xxx
Country 2 vs. Reference Country	xx.x (xx.x-xx.x)	0.xxx	xx.x (xx.x-xx.x)	0.xxx
Country Y vs. Reference Country	xx.x (xx.x-xx.x)	0.xxx	xx.x (xx.x-xx.x)	0.xxx
Tumour type		0.xxx		0.xxx
Rectal cancer vs. Dukes C colon cancer	xx.x (xx.x-xx.x)	0.xxx	xx.x (xx.x-xx.x)	0.xxx
High risk Dukes B colon cancer vs. Dukes C colon cancer	xx.x (xx.x-xx.x)	0.xxx	xx.x (xx.x-xx.x)	0.xxx
Adjuvant chemotherapy (exposed vs. not exposed to Oxaliplatin)	xx.x (xx.x-xx.x)	0.xxx	xx.x (xx.x-xx.x)	0.xxx
Overall survival				
Treatment (Aspirin vs. placebo)	xx.x (xx.x-xx.x)	0.xxx	xx.x (xx.x-xx.x)	0.xxx
Country		0.xxx		0.xxx
Country 1 vs. Reference Country	xx.x (xx.x-xx.x)	0.xxx	xx.x (xx.x-xx.x)	0.xxx
Country 2 vs. Reference Country	xx.x (xx.x-xx.x)	0.xxx	xx.x (xx.x-xx.x)	0.xxx
Country Y vs. Reference Country	xx.x (xx.x-xx.x)	0.xxx	xx.x (xx.x-xx.x)	0.xxx

Tumour type					
Rectal cancer vs. Dukes C colon cancer			0.xxx		0.xxx
High risk Dukes B colon cancer vs. Dukes C colon cancer	xx.x (xx.x-xx.x)		0.xxx	xx.x (xx.x-xx.x)	0.xxx
Adjuvant chemotherapy (exposed vs. not exposed to Oxaliplatin)	xx.x (xx.x-xx.x)		0.xxx	xx.x (xx.x-xx.x)	0.xxx

Note: Adjusted hazard ratio was estimated using Cox proportional hazard model with trial stratification factors (centre pooled by country (categorical), type of tumour (categorical) and type of adjuvant chemotherapy (categorical)) as covariates.

Table 9: Summary of adverse events

Population: Safety population

	Number of Subjects		Number of Events	
	Aspirin (N=xxxx)	Placebo (N=xxxx)	Aspirin	Placebo
Subjects ever experienced any AE, n (%)	xxx (xx.x)	xxx (xx.x)	xxx	xxx
Severity, n (%)				
Mild	xxx (xx.x)	xxx (xx.x)	xxx	xxx
Moderate	xxx (xx.x)	xxx (xx.x)	xxx	xxx
Severe	xxx (xx.x)	xxx (xx.x)	xxx	xxx
Unknown	xxx (xx.x)	xxx (xx.x)	xxx	xxx
Treatment related, n (%)				
Not related	xxx (xx.x)	xxx (xx.x)	xxx	xxx
Unlikely related	xxx (xx.x)	xxx (xx.x)	xxx	xxx
Possibly related	xxx (xx.x)	xxx (xx.x)	xxx	xxx
Probably related	xxx (xx.x)	xxx (xx.x)	xxx	xxx
Definitely related	xxx (xx.x)	xxx (xx.x)	xxx	xxx
Unknown	xxx (xx.x)	xxx (xx.x)	xxx	xxx
Treatment given, n (%)				
Yes	xxx (xx.x)	xxx (xx.x)	xxx	xxx
No	xxx (xx.x)	xxx (xx.x)	xxx	xxx
Outcome, n (%)				
Recovered	xxx (xx.x)	xxx (xx.x)	xxx	xxx
Recovered with sequelae	xxx (xx.x)	xxx (xx.x)	xxx	xxx
Ongoing	xxx (xx.x)	xxx (xx.x)	xxx	xxx
Death	xxx (xx.x)	xxx (xx.x)	xxx	xxx
Unknown	xxx (xx.x)	xxx (xx.x)	xxx	xxx
Action taken to study treatment, n (%)				
None	xxx (xx.x)	xxx (xx.x)	xxx	xxx
Modified	xxx (xx.x)	xxx (xx.x)	xxx	xxx
Temporarily interrupted	xxx (xx.x)	xxx (xx.x)	xxx	xxx
Permanently discontinued	xxx (xx.x)	xxx (xx.x)	xxx	xxx
Unknown	xxx (xx.x)	xxx (xx.x)	xxx	xxx

AE: adverse event.

Note: Under number of events, the same AE term of multiple severities, relationships, treatments, actions reported by a single subject will be counted separately. Under number of subjects, only unique subjects will be counted.

Table 10: Summary of serious adverse events

Population: Safety population

	Number of Subjects		Number of Events	
	Aspirin (N=xxxx)	Placebo (N=xxxx)	Aspirin	Placebo
Subjects ever experienced any SAE, n (%)	xxx (xx.x)	xxx (xx.x)	xxx	xxx
SAE criteria, n (%)				
Death	xxx (xx.x)	xxx (xx.x)	xxx	xxx
Life-threatening	xxx (xx.x)	xxx (xx.x)	xxx	xxx
Inpatient hospitalization	xxx (xx.x)	xxx (xx.x)	xxx	xxx
Hospitalization prolonged	xxx (xx.x)	xxx (xx.x)	xxx	xxx
Disability / incapacity	xxx (xx.x)	xxx (xx.x)	xxx	xxx
Congenital anomaly	xxx (xx.x)	xxx (xx.x)	xxx	xxx
Others	xxx (xx.x)	xxx (xx.x)	xxx	xxx
Action taken, n (%)				
None	xxx (xx.x)	xxx (xx.x)	xxx	xxx
Modified to 100mg OD	xxx (xx.x)	xxx (xx.x)	xxx	xxx
Temporarily interrupted	xxx (xx.x)	xxx (xx.x)	xxx	xxx
Permanently discontinued	xxx (xx.x)	xxx (xx.x)	xxx	xxx
Unknown	xxx (xx.x)	xxx (xx.x)	xxx	xxx
Treatment related, n (%)				
Not related	xxx (xx.x)	xxx (xx.x)	xxx	xxx
Unlikely related	xxx (xx.x)	xxx (xx.x)	xxx	xxx
Possibly related	xxx (xx.x)	xxx (xx.x)	xxx	xxx
Probably related	xxx (xx.x)	xxx (xx.x)	xxx	xxx
Definitely related	xxx (xx.x)	xxx (xx.x)	xxx	xxx
Unknown	xxx (xx.x)	xxx (xx.x)	xxx	xxx
Outcome, n (%)				
Recovered	xxx (xx.x)	xxx (xx.x)	xxx	xxx
Recovered with sequelae	xxx (xx.x)	xxx (xx.x)	xxx	xxx
Ongoing	xxx (xx.x)	xxx (xx.x)	xxx	xxx
Death	xxx (xx.x)	xxx (xx.x)	xxx	xxx
Unknown	xxx (xx.x)	xxx (xx.x)	xxx	xxx
Withdrawn due to SAE, n (%)				
Yes	xxx (xx.x)	xxx (xx.x)	xxx	xxx
No	xxx (xx.x)	xxx (xx.x)	xxx	xxx
Causality, n (%)				
Study treatment	xxx (xx.x)	xxx (xx.x)	xxx	xxx

Disease under study	xxx (xx.x)	xxx (xx.x)	xxx	xxx
Other illness	xxx (xx.x)	xxx (xx.x)	xxx	xxx
Concurrent medication / treatment	xxx (xx.x)	xxx (xx.x)	xxx	xxx
Others	xxx (xx.x)	xxx (xx.x)	xxx	xxx
Unknown	xxx (xx.x)	xxx (xx.x)	xxx	xxx

SAE: serious adverse event.

Note: Under number of events, the same SAE term of multiple SAE criteria, actions, relationships, outcomes and causalities reported by a single subject will be counted separately. Under number of subjects, only unique subjects will be counted.

Table 11: Adverse events by system organ class and severity grade

Population: Safety population

System Organ Class Preferred Term	MILD			MODERATE			SEVERE			UNKNOWN		
	n (%)	nAE	n (%)	n (%)	nAE	n (%)	n (%)	nAE	n (%)	n (%)	nAE	n (%)
Aspirin (N = xxx)												
System organ class 1	xx (xx.x)	xx	xx (xx.x)	xx	xx	xx (xx.x)	xx	xx	xx (xx.x)	xx	xx	xx (xx.x)
Preferred term 1	xx (xx.x)	xx	xx (xx.x)	xx	xx	xx (xx.x)	xx	xx	xx (xx.x)	xx	xx	xx (xx.x)
Preferred term 2	xx (xx.x)	xx	xx (xx.x)	xx	xx	xx (xx.x)	xx	xx	xx (xx.x)	xx	xx	xx (xx.x)
Preferred term 3	xx (xx.x)	xx	xx (xx.x)	xx	xx	xx (xx.x)	xx	xx	xx (xx.x)	xx	xx	xx (xx.x)
...	xx (xx.x)	xx	xx (xx.x)	xx	xx	xx (xx.x)	xx	xx	xx (xx.x)	xx	xx	xx (xx.x)
System organ class X	xx (xx.x)	xx	xx (xx.x)	xx	xx	xx (xx.x)	xx	xx	xx (xx.x)	xx	xx	xx (xx.x)
Preferred term X	xx (xx.x)	xx	xx (xx.x)	xx	xx	xx (xx.x)	xx	xx	xx (xx.x)	xx	xx	xx (xx.x)

Placebo
(N = xxx)

System Organ Class Preferred Term	MILD			MODERATE			SEVERE			UNKNOWN		
	n (%)	nAE	n (%)	n (%)	nAE	n (%)	n (%)	nAE	n (%)	n (%)	nAE	n (%)
System organ class 1	xx (xx.x)	xx	xx (xx.x)	xx	xx	xx (xx.x)	xx	xx	xx (xx.x)	xx	xx	xx (xx.x)
Preferred term 1	xx (xx.x)	xx	xx (xx.x)	xx	xx	xx (xx.x)	xx	xx	xx (xx.x)	xx	xx	xx (xx.x)

Preferred term 2	XX (XX.X)	XX	XX (XX.X)	XX	XX (XX.X)	XX	XX (XX.X)	XX
Preferred term 3	XX (XX.X)	XX	XX (XX.X)	XX	XX (XX.X)	XX	XX (XX.X)	XX
...	XX (XX.X)	XX	XX (XX.X)	XX	XX (XX.X)	XX	XX (XX.X)	XX
System organ class X	XX (XX.X)	XX	XX (XX.X)	XX	XX (XX.X)	XX	XX (XX.X)	XX
Preferred term X	XX (XX.X)	XX	XX (XX.X)	XX	XX (XX.X)	XX	XX (XX.X)	XX

n (%) = number (percent) of subjects.

nAE = number of adverse events.

Table 12: Serious adverse events by system organ class

System Organ Class Preferred Term	Aspirin (N = xxx)		Placebo (N = xxx)	
	n (%)	nAE	n (%)	nAE
System organ class 1	xx (xx.x)	xx	xx (xx.x)	xx
Preferred term 1	xx (xx.x)	xx	xx (xx.x)	xx
Preferred term 2	xx (xx.x)	xx	xx (xx.x)	xx
Preferred term 3	xx (xx.x)	xx	xx (xx.x)	xx
...				
...				
System organ class X	xx (xx.x)	xx	xx (xx.x)	xx
Preferred term X	xx (xx.x)	xx	xx (xx.x)	xx

n (%) = number (percent) of subjects.

nAE = number of adverse events.

Table 13: Severe adverse events related to treatment by system organ class

System Organ Class Preferred Term	Population: Safety population			
	Aspirin (N = xxx)		Placebo (N = xxx)	
	n (%)	nAE	n (%)	nAE
System organ class 1	xx (xx.x)	xx	xx (xx.x)	xx
Preferred term 1	xx (xx.x)	xx	xx (xx.x)	xx
Preferred term 2	xx (xx.x)	xx	xx (xx.x)	xx
Preferred term 3	xx (xx.x)	xx	xx (xx.x)	xx
...				
...				
System organ class X	xx (xx.x)	xx	xx (xx.x)	xx
Preferred term X	xx (xx.x)	xx	xx (xx.x)	xx

Related adverse events are defined as those with “Unknown”, “Possible”, “Probable”, “Definite” relationship with study treatment.

n (%) = number (percent) of subjects.

nAE = number of adverse events.

Table 14: Medical events
Population: Safety population

n (%)	Aspirin (N=xxxx)	Placebo (N=xxxx)	P-value ¹
Acute myocardial infarct			0.xxx
Yes	xx (xx.x)	xx (xx.x)	
No	xx (xx.x)	xx (xx.x)	
Ischaemic stroke			0.xxx
Yes	xx (xx.x)	xx (xx.x)	
No	xx (xx.x)	xx (xx.x)	
New cancer (non-colorectal)			0.xxx
Yes	xx (xx.x)	xx (xx.x)	
No	xx (xx.x)	xx (xx.x)	
Major GI bleeding			0.xxx
Yes	xx (xx.x)	xx (xx.x)	
No	xx (xx.x)	xx (xx.x)	
Hemorrhagic stroke			0.xxx
Yes	xx (xx.x)	xx (xx.x)	
No	xx (xx.x)	xx (xx.x)	
Major nervous system bleeding			0.xxx
Yes	xx (xx.x)	xx (xx.x)	
No	xx (xx.x)	xx (xx.x)	

n: number of subjects; %: percentage of randomised in each treatment group; GI: gastrointestinal bleeding.
¹Fisher's exact test.

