4 STATISTICAL ANALYSIS

4.1 General

Continuous variables will be summarised using descriptive statistics, i.e., mean, standard deviation, median, interquartile range (IQR), minimum and maximum. Categorical variables will be summarised by frequency and percentage. All statistical significance tests and confidence intervals are two-sided. A p-value <0.05 is considered statistically significant. All confidence intervals (CIs) are at 95% level. All statistical analyses will be conducted using SAS version 9.2 or higher (Statistical Analysis System software, SAS Institute, North Carolina, USA).

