4.6 Time-to-event Endpoints

For primary outcome of DFS, survival curves will be constructed using the Kaplan-Meier method. Product-limit estimates of 3- and 5-year survival rates will be calculated. Median survival times will also be reported. The complementary log-log transformation will be used for deriving the median survival times corresponding 95% CIs. The primary analysis will be a mITT analysis which uses stratified logrank test adjusting for trial stratification factor

(centre pooled by country (categorical), type of tumour (Dukes C colon vs. high risk Dukes B colon vs. rectal; categorical) and type of adjuvant chemotherapy (exposed vs. not exposed to Oxaliplatin; categorical)) to generate p-value comparing the treatment groups, followed by multivariate Cox proportional hazard (PH) regression model to estimate adjusted HR and its corresponding 95% CI. The multivariate Cox PH regression model will also include the trial stratification factors used in the stratified logrank test as covariates. Additional covariates such as time from surgery to first chemotherapy in days (continuous), type of surgery (laparoscopic surgery vs. open surgery; categorical), chemotherapy duration (<3 months vs. 3-6 months vs. >6 months; categorical) and age group (<70 vs. ≥ 70 years old; categorical) will be added as part of sensitivity analysis. The CI of the HR will be based on profile-likelihood. Firth's correction may be used if monotone likelihood phenomenon is observed. Unadjusted HR and p-value from non-stratified logrank test will also be reported as supplementary results.

As part of secondary objective, the same analysis on DFS will be repeated for sub-population of colon cancer except that the covariate, type of tumour, will consist of only two categories: Dukes C colon vs. high risk Dukes B colon.

The secondary outcome of OS will be analysed in a similar manner as the primary endpoint, except that repeated analysis on colon cancer sub-population will not be done.

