For all subgroup analyses of DFS and OS by different countries, tumour types (high risk Dukes B colon, Dukes C colon, colon, rectal), adjuvant chemotherapy types (exposed to Oxaplatin, not exposed to Oxaliplatin), ethnic groups (East Asian, South Asian, Caucasian, Others), type of surgery (laparoscopic surgery, open surgery), chemotherapy duration (<3 months, 3-6 months, >6 months), age group (<70, ≥ 70), levels of compliance (<70%, $\geq 70\%$), duration of exposure to drug (<1 year, 1-2 years, >2 years), PIK3CA mutations (mutant PIK3CA, wild-type PIK3CA) and COX-2 expression (positive for COX-2 overexpression, negative for COX-2 overexpression), tests for interactions between treatment group and the subgroup variable of interest will be conducted first. As the subgroups under tumour types are not mutually exclusive, the test for interaction will be based on the original mutually

exclusive groups. Results of subgroup analyses will be presented in forest plots. Subgroup analyses will be considered as exploratory.

Appropriateness of Cox PH regression model will be checked using graphical method of log-log survival curves for treatment indicator and each covariate. Continuous covariate will be dichotomised at mean value to check for the PH assumption. PH assumption will be considered not satisfied if there is strong evidence of non-parallelism in the log-log survival curves. Should there be at least one covariate not satisfying the PH assumption, “no-interaction” (i.e. estimated coefficients not varying by stratum) stratified Cox regression model will be used instead. The model will be stratified by strata formed after combining categories of all covariates which did not satisfy the PH assumption. Covariate(s) which satisfies the PH assumption will remain included in the stratified model. If the treatment indicator is found to not satisfy the PH assumption, time-varying HR will be obtained by partitioning the follow-up time into 1-year intervals.

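### Table 7 footnote 3 takes the sensitivity p-value from a log-rank test stratified by all seven model covariates, one of them continuous in days, so it can contradict the confidence interval beside it

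*SAP*

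**What the plan says.** SAP 4.6 has two layers. For the main result, "The primary analysis will be a mITT analysis which uses stratified logrank test adjusting for trial stratification factor", the factors being country (pooled centres), tumour type and oxaliplatin exposure. A Cox model with the same three factors as covariates gives the hazard ratio. The Cox model is then extended for sensitivity: "Additional covariates such as time from surgery to first chemotherapy in days (continuous), type of surgery", together with chemotherapy duration and age group. Section 4.6 describes no log-rank test stratified by these four additions. On intervals it says: "The CI of the HR will be based on profile-likelihood".

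Mock Table 7 in Appendix 1 reports the extended model in rows such as "Adjusted DFS hazard ratio 2 (95% CI); p-value". Footnote 3 defines that row. It lists the three trial factors and the four additions, with timing left ungrouped: "time from surgery to first chemotherapy in days (continuous), type of surgery (categorical". It then gives the source of the p-value: "chemotherapy duration (categorical) and age group (categorical) as covariates. P-values from stratified log-rank test stratified by the factors included as covariates". Footnote 2 has the same p-value sentence for the three-factor model.

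The only rule for cutting a continuous variable is in the proportional hazards paragraph of 4.6: "Continuous covariate will be dichotomised at mean value to check for the PH assumption". SAP 4.1 sets the significance rule: "A p-value <0.05 is considered statistically significant".

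**The concern.** The sentence works in footnote 2 because all three covariates there are categorical. Carried over to footnote 3, it asks for strata formed by seven variables, one of them measured in days. A stratified log-rank test learns from an event only if patients from both arms are at risk in that stratum at that time. Day-level strata mostly hold one patient, so most events contribute nothing. The hazard ratio and interval in the same cell come from a Cox model that uses every event.

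At stake are six printed p-values: DFS, OS and colon-only DFS, each in the modified intention-to-treat and per-protocol sets. A real effect could appear to vanish after adjustment only because the strata are nearly empty. No other table would correct this, because Table 8 gives model p-values for the three-factor Cox model only.

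**Working it through.** **Inputs from the documents.** Two-sided 5% level (SAP 4.1). Hazard ratio 0.72, 300 events, 80% power, pooled 5-year DFS 79%, 10% attrition and 1587 patients (SAP 3.5). Allocation 1:1 (SAP 3.1). Covariates from Table 7 footnote 3.

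**The plan's own figures reproduce.**
- Schoenfeld: 4 × (1.960 + 0.842)² / (ln 0.72)² = 4 × 7.85 / 0.1079 = 291 events.
- Freedman: 7.85 × (1.72 / 0.28)² gives 297 events. Both are close to 300.
- Power with 300 events: Φ(√300 × 0.3285 / 2 − 1.960) = 0.812.
- Sample size: 300 / (0.21 × 0.90) = 1587.3.

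None of these is disputed; they set the scale.

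**Number of strata.** Tumour type, oxaliplatin, surgery type, chemotherapy duration and age group give 3 × 2 × 2 × 3 × 2 = 72 cells per country. Five country groups would give 5 × 72 = 360 cells before days are added, for 1587 patients.

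**Why events are lost.** An event with r patients at risk in its stratum, r₁ of them on aspirin, adds variance (r₁/r)(1 − r₁/r). This is zero when only one arm is at risk. With E informative events, power is roughly Φ(√E × 0.3285 / 2 − 1.960):
- E = 60 (20% of 300): 0.246
- E = 30 (10%): 0.144
- E = 15 (5%): 0.093

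**Simulation at hazard ratio 0.72.** The documents do not give the number of country groups, the spread of days or the covariate prevalences. Two sets of assumptions were used.
- *Set A*: 18 settings × 600 replicates. 5, 6 or 10 country groups; days with mean 45 and SD 7, 14 or 21; tumour type 50/20/30%; oxaliplatin 70%; laparoscopic 50%; chemotherapy duration 5/70/25%; age 70 or over 15%; blocks of 4 within the trial strata; follow-up 2–7 years with about 10% dropout over 5 years.
- *Set B*: 4 settings × 150 replicates. 5 or 11 unequal country groups; days with mean 42 and SD 7 or 15; similar prevalences; mild prognostic effects; exactly 300 events; Wald test for the Cox model.

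| Test | Power, A | Power, B | Informative events of 300, B | Verdict differs from Cox CI, B |
|---|---|---|---|---|
| Log-rank, three trial factors | 77–83% | 78–82% | 298–300 | 3–5% |
| Log-rank, six categorical covariates | 63–75% | 66–77% | 246–274 | 9–20% |
| Log-rank, plus days split at mean | 54–68% | 63–72% | 210–249 | 12–21% |
| Log-rank, plus days as they stand | 8–23% | 15–29% | 30–81 | 56–66% |
| Seven-covariate Cox model | 78–84% | 79–81% | all | – |

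The first row is compared with the three-factor Cox interval, the other log-rank rows with the seven-covariate one. On the literal reading, set A had 1218–1507 strata, 61–90% of patients alone in theirs, and 4–20% of events with both arms at risk. Further runs with A's prevalences, no prognostic effects and about 288 events gave 6–25% power.

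**Contradiction within a cell.** Given that the Cox interval excludes 1, the log-rank p-value is 0.05 or more in these proportions of runs:
- Literal reading: 74–91% in A. In B, from 0.527 / 0.787 = 67% to 0.660 / 0.807 = 82%.
- Six categorical covariates only: 13–24% in A.
- Footnote 2 as planned, against its own Cox model: in B, from 0.007 / 0.800 = 0.9% to 0.027 / 0.800 = 3.4%.

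**Other rows, literal reading against the Cox model.** Colon DFS (assumed 1058 patients, 200 events): 9–15% against 63–66%. OS (assumed 120–180 events, hazard ratio 0.72): 8–13% against 45–63%. The per-protocol set was not simulated.

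**No treatment effect.** At hazard ratio 1 the literal test rejects in 4.9–5.1% of runs in A and about 4% in B.

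**The case against.** The best defence is that footnote 3 does not mean what it literally says. Within it, the word for factors is otherwise attached to the trial stratification factors, and 4.6 defines only a three-factor stratified log-rank test. On that reading no power is lost. Labelling days as continuous in the same footnote also suggests that day-level strata were not intended, and a programmer faced with more than a thousand strata would probably stop. In addition, a log-rank p-value beside a Cox interval is the SAP's deliberate choice for the primary result too. These are sensitivity rows, no decision rule uses this p-value, and the simulated percentages depend on assumed distributions.

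Much of this stands. The literal reading is the worst case, and the ranges are not bounds: A and B overlap but neither contains the other. The mismatch under footnote 2 is small, by design, and not challenged here.

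It does not save the footnote. With three factors only, the p-value beside adjusted hazard ratio 2 merely repeats the one beside adjusted hazard ratio 1 and does not test the estimate it accompanies. With the categorical covariates only, power still falls and the test omits a covariate that the model uses. If a programmer does notice, the test is then chosen without a pre-specified rule.

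**Conclusion.** The concern holds: footnote 3 is wrong as written and should be corrected. Across all the DFS simulations, the literal reading gives 6–29% power where the extended Cox model has 78–84%, and in most runs with a Cox interval excluding 1 it prints a non-significant p-value beside it. The exact percentages rest on assumed country groups, spread of days and prevalences, with Monte Carlo error of up to about 4 percentage points in set B. The direction was the same in every setting with a treatment effect. The harm is lost power and contradictory output, confined to six sensitivity p-values. The primary p-value, every hazard ratio and every interval are unaffected, and there is no inflation of type I error.

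**What to change.** Replace the last sentence of Table 7 footnote 3 so that the p-value is the treatment test from the same Cox model that gives adjusted hazard ratio 2. The likelihood-ratio test fits best: a 95% profile-likelihood interval excludes 1 exactly when that test gives p below 0.05, so the two entries cannot disagree. If Firth's correction is used, as 4.6 allows, use the penalised version of the test; if the stratified Cox fallback is used, take the p-value from that model. Leave footnote 2 and its three-factor stratified log-rank test unchanged.

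The cost is one sentence. The model is already planned and no new data are needed. The Cox p-value relies on proportional hazards, which 4.6 already checks.
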